- *This is a “Multi-Site Study that involves more than one site performing ALL aspects of the research procedures as outlined above.” OR “This is a Collaborative Study that involves UT Austin researchers working with external researchers who are engaged in performing the following study activities (list activities).”*
- *For assistance with Multi-Site/Collaborative research, review [UT Guidance: Submitting Studies Relying on UT IRB](#), download HRP-UT932 Request to Rely Assessment Form from the [UTRMS-IRB Library](#) and email [contact].*

This is a single site, randomized, double-blind, placebo-controlled study to evaluate the efficacy of lumateperone as an adjunctive treatment of patients with MDD and a history of early childhood abuse. During the study subjects currently receiving approved dosing regimen of ADT, who experience an inadequate therapeutic response according to MADRS score at Baseline, will be randomized in a 1:1 ratio to Lumateperone 42mg or placebo, and receive treatment for 6 weeks. The primary efficacy analysis will be based on the week 6 assessment of the primary and secondary efficacy endpoints. The overall duration of the study, including Screening and intervention period, will be approximately 9 weeks per subject: a 2-week screening period, 6 weeks of double-blind treatment, and a 1-week safety follow-up visit.

The study design is presented in Figure 1.

Figure 1.

The study will be conducted as follows:

- Screening Period (2 weeks):
- A 2-week Screening Period during which patient eligibility will be assessed. After obtaining written informed consent, diagnostic interviews and physical examinations will be conducted, vital signs and ECGs will be assessed, and blood and urine samples will be collected for laboratory assessments. With the exception of stable, allowed concomitant medications, patients must discontinue prohibited psychotropic drugs during the Screening Period. The following rating scales will be administered.

Clinician Rater: CAPS-5, MADRS, DIAMOND, SCID-5 Borderline Personality module, CGI-S, MGH-ATRQ, CSSRS

PROS, GAD-7, QIDS-SR-16, EQ 5D-5L, CTQ, GASS, PCL-5, NWS, MCI

Once deemed eligible, the subject will also be offered to enroll in the optional EMA wellness app to be completed 3X daily from screening visit to the end of study visit

- Double-blind Treatment Period (DBTP, 6 weeks):

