4.2 Order of Assessments

4.2.1 Screening (Visit-1 Week-2)

All subjects agreeing to participate in the study must give informed consent by signing the ICF before any study-related procedures are performed. Screening begins after ICF has been signed and dated by the subject and the Investigator or other appropriate site staff. The duration of the Screening will be 2 weeks.

The following procedures should be performed in order after the ICF is reviewed and signed:

1. Collection of medical and psychiatric history, concomitant medications and demographic information. Physical examination, ECG and pulse oximetry need to be performed, and height, weight, BMI and vital signs recorded.
2. Standardized assessments to include:
Clinician Rater: CAPS-5, MADRS, DIAMOND, SCID borderline personality module, CGI-S, MGH-ATRQ, CSSRS
PROs: GAD-7, QIDS-SR-16, EQ 5D-5L, CTQ, PCL-5, NSW, MCI
3. Collection of urine sample for urinalysis and drug screen analysis.

4. Blood sample collection to obtain hematology, biochemistry, hepatitis B and C, HIV, TSH and FSH data. A serum pregnancy test (b-HCG) is performed at screening for females of childbearing potential.
5. Breath alcohol test.
6. EMA wellness app activation

Subjects that meet all eligibility and inclusion and no exclusion criteria, will undergo Visit 2 (Baseline).

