4.2.2 Baseline (Visit 2 Week-1)

Subjects continuing to meet all eligibility and inclusion criteria and no exclusion criteria, will be randomized within each group at Baseline to start the study treatment.

1. Assessment scales: MADRS, CGI-S C-SSRS, HAMD-17, GAD-7, PHQ-9, QIDS-SR-16, and EQ 5D-5L.
2. Vital signs, including body temperature, systolic and diastolic BP, HR, pulse oximetry, and RR measures after the subject has been resting for at least 3 minutes.
3. ECGs taken pre-dose.
4. fMRI will be obtained.
5. EMA wellness App
6. AE if applicable
7. Laboratory tests, consisting of: blood sample for Hematology
8. POC: Urine drug test, pregnancy test (if applicable) and Breath Alcohol test

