4.2.3 Double-blind Treatment Visits (Visits 3-7 ;Weeks 2-6)

1. Record AEs as reported by patient or observed by Investigator
2. Review concomitant medications
3. Study drug compliance check, return unused Meds at each visit
4. Vital signs (BP, pulse rate, body temperature, respiratory rate) and weight
5. Assessment Scales: MADRS, CGI-S C-SSRS, HAMD-17, GAD-7, PHQ-9, QIDS-SR-16, EQ 5D-5L and GASS
6. Lab tests for Hematology for CBC will be completed at wee4 and week6 visits and Complete BW similar to screening visit will be completed at Week-7
7. EMA Wellness App (Optional)

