7.6 Extrapyramidal Symptom Assessment

Glasgow Antipsychotic symptom scale: The Glasgow Antipsychotic Side-effect Scale is a patient self-report scale used to screen for antipsychotic side effects.²⁴

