9.1 Adverse Event Definition

An AE is any untoward medical occurrence in a study subject administered a pharmaceutical product and may not necessarily have a causal relationship with the administered treatment. An AE can therefore be any unfavorable and unintended sign (including a clinically significant laboratory abnormality, for example), symptom, or disease temporally associated with the use of a medicinal (investigational) product, regardless of its relationship to the medicinal (investigational) product. During the study, an AE can also occur outside the time that the study drug(s) was given (e.g., during the time from discontinuation of prohibited medications). Preexisting conditions, diseases, or disorders are not considered AEs unless there is a change in severity, frequency, or quality.

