If your study includes identifying potential participants using PHI (e.g., a partial HIPAA waiver for recruitment is needed), note this here and be sure you have completed item 12 in the [Study Elements](#) section of this form to request a waiver.

Other recruitment material/method

Department referral registry
2020040046 (IRB number)

28. Screening Procedures

Describe the procedures to screen individuals to determine whether inclusion/exclusion criteria are met. Be sure to specify the following specific details:

- Will screening procedures occur before or after consent?
- For any screening data collected prior to consent, how will this data be used? For example, will it be used only to confirm eligibility, screen failure analyses, or will it be used to answer the research questions as well?

Please upload all screening questionnaires/tools in the "Other Attachments" section in UTRMS.

- A 2-week Screening Period during which patient eligibility will be assessed. After obtaining written informed consent, diagnostic interviews and physical examinations will be conducted, vital signs and ECGs will be assessed, and blood and urine samples will be collected for laboratory assessments. With the exception of stable, allowed concomitant medications, patients must discontinue prohibited psychotropic drugs during the Screening Period. The following rating scales will be administered.

Clinician Rater: CAPS-5, MADRS, DIAMOND, SCID-5 Borderline Personality module, CGI-S, MGH-ATRQ, CSSRS

PROs, GAD-7, QIDS-SR-16, EQ 5D-5L, CTQ, GASS, PCL-5, NWS

Once deemed eligible, the subject will also be offered to enroll in the optional EMA wellness app to be completed 3x daily from screening visit to the end of study visit

Consent /Assent Pathways

29. Consent Pathways

Obtaining informed consent is the default expectation for enrolling subjects to your research. For all human subjects included in the research (either via direct participation or having their private, identifiable data included in the study), researchers must have a pathway either to obtain informed consent or request and meet criteria for waiving informed consent.

Select all consent pathways that will be used to enroll subjects into the study.

Examples:

- 1) If you will obtain consent from one group of adult participants but are requesting a waiver for another group (such as a retrospective chart review group), both "Obtaining Consent from Adult Participants" and "Requesting Waiver" should be checked.

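### The protocol contradicts itself on whether the GASS is given before the first dose; if Table 1 is followed, its only named side-effect and extrapyramidal scale has no baseline

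*Protocol*

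**What the plan says.** Two places put the GASS at Screening. The Screening Period text under item 7 (Study Procedure Description) lists "PROS, GAD-7, QIDS-SR-16, EQ 5D-5L, CTQ, GASS, PCL-5, NWS, MCI". Item 28 (Screening Procedures) lists "PROs, GAD-7, QIDS-SR-16, EQ 5D-5L, CTQ, GASS, PCL-5, NWS".

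Three places do not have it before dosing:

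- Section 4.2.1 (Screening) gives "PROs: GAD-7, QIDS-SR-16, EQ 5D-5L, CTQ, PCL-5, NSW, MCI", almost the same list without the GASS.
- Section 4.2.2 (Baseline, Visit 2) gives "Assessment scales: MADRS, CGI-S C-SSRS, HAMD-17, GAD-7, PHQ-9, QIDS-SR-16, and EQ 5D-5L".
- In Table 1 the GASS row is blank at Visits 1 and 2 and marked at Visits 3, 5, 7 and 8.

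For the treatment visits, section 4.2.3 gives "Assessment Scales: MADRS, CGI-S C-SSRS, HAMD-17, GAD-7, PHQ-9, QIDS-SR-16, EQ 5D-5L and GASS" for Visits 3 to 7 with no restriction by visit. The Visit 8 list (section 7.2.4) does not include the GASS.

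Section 7.6 (Extrapyramidal Symptom Assessment) names no other instrument and calls the GASS a "patient self-report scale used to screen for antipsychotic side effects". Under item 7, the first dose is taken on the evening of the Baseline visit.

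**The concern.** Section 1.1.1 gives efficacy and safety as the purpose of the study, and the GASS is the one scored instrument for antipsychotic side effects. All patients stay on a stable antidepressant (inclusion criterion 6), and some stop prohibited psychotropics during Screening. Complaints of the kind a side-effect scale picks up are therefore plausible before any study drug is taken. A pre-dose score shows which of these a patient already had.

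Table 1 and section 4.2 are the parts of the protocol that sites work from. If they prevail, the first GASS comes about a week into dosing, and no later analysis can recover the missing value. Section 9.1 adds some weight: "Preexisting conditions, diseases, or disorders are not considered AEs unless there is a change in severity, frequency, or quality". A complaint first raised by the GASS at Visit 3 would have no earlier GASS score to compare with.

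**Working it through.** **1. Is the blank in Table 1 real?** The table has eight visit columns. The MADRS row is marked in all eight, which fixes the alignment. Read against it, the GASS row is marked in columns 3, 5, 7 and 8. Sections 4.2.1 and 4.2.2 omit the GASS independently, so this is not an artefact of text extraction.

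**2. GASS entries side by side**

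| Visit | Table 1 | Text |
|---|---|---|
| 1 Screening | no | items 7 and 28: yes; section 4.2.1: no |
| 2 Baseline | no | section 4.2.2: no |
| 3 | yes | section 4.2.3: yes |
| 4 | no | section 4.2.3: yes |
| 5 | yes | section 4.2.3: yes |
| 6 | no | section 4.2.3: yes |
| 7 | yes | section 4.2.3: yes |
| 8 | yes | section 7.2.4: no |

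Dosing starts on the evening of Visit 2, so every GASS in Table 1 is post-dose.

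**3. What a missing baseline costs in precision.** The protocol states no figure for the GASS (no SD, effect size or power), so there is nothing to reproduce. Inputs: n = 25 per arm (items 6 and 15); two-sided 5% level, 80% power and pre/post correlation r = 0.3, 0.5 and 0.7, all assumed. Results are in units of the GASS standard deviation, using the normal approximation.

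- Post-dose values only: SE = √(2/n) = √(2/25) = 0.283. Detectable effect = (1.960 + 0.842) × 0.283 = 0.79 SD.
- Adjusted for a pre-dose value: SE = √((1 − r²) × 2/n), with the same multiplier.

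| Analysis | SE (SD) | Detectable effect, 80% power (SD) | Power for an assumed 0.8 SD effect |
|---|---|---|---|
| No pre-dose GASS | 0.283 | 0.79 | 81% |
| Adjusted, r = 0.3 | 0.270 | 0.76 | 84% |
| Adjusted, r = 0.5 | 0.245 | 0.69 | 90% |
| Adjusted, r = 0.7 | 0.202 | 0.57 | 98% |

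**4. Chance imbalance.** The difference between arms in mean pre-dose GASS has SE 0.283 SD under randomisation. The probability that it exceeds 0.5 SD in either direction is 2 × (1 − Φ(0.5/0.283)) = 2 × (1 − Φ(1.77)) ≈ 0.08. Without a pre-dose score, such an imbalance could be neither seen nor adjusted for.

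**The case against.** A reader might infer that drug effects cannot be separated from symptoms already present. The documents do not support this. The trial is randomised 1:1, double-blind and placebo-controlled, and both arms keep their antidepressant. Background symptoms are balanced in expectation, so the post-dose difference between arms estimates the average drug effect on the GASS without bias.

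A reader might also infer that the adverse event rule in section 9.1 cannot be applied. That goes too far as well. Section 9.1 does not refer to the GASS, and pre-dose status is recorded elsewhere. Item 43a collects adverse events from consent, puts those arising before the end of screening in the medical history, documents pre-existing conditions, and includes a neurological examination. Section 3.7 records prior medications and therapies. The investigator judges severity and causality for each event (section 9.3.1). These records are not a scored scale, and they capture a complaint only if it was raised or found at the time, so the GASS baseline would add to them but is not indispensable.

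Two further objections stand. The loss arises only if Table 1 and section 4.2 are followed; under items 7 and 28 a pre-dose GASS exists. And the GASS is in no aim, estimand or stated analysis, so the precision figures illustrate what a baseline is worth and do not describe a planned test. How the GASS is analysed may properly be left to the statistical analysis plan.

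None of this removes the contradiction, and an analysis plan cannot supply a value that was never collected.

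**Conclusion.** The protocol gives incompatible instructions on a pre-dose GASS. If Table 1 is followed, three things are lost on this scale: change from before treatment within a patient, identification of symptoms that arose on treatment in a given patient, and a check of baseline balance. The comparison between arms remains valid but is less precise: 0.79 SD detectable, against 0.76 to 0.57 SD with a baseline. That range rests wholly on the assumed correlation of 0.3 to 0.7 and on 25 evaluable patients per arm. At the lower end the gain is slight; at the upper end it is substantial. The case for acting rests mainly on the individual-level information, which cannot be obtained afterwards, and on the very low cost of collecting it.

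**What to change.** Mark a pre-dose GASS in Table 1 and in the matching visit list. This can be section 4.2.1 (Screening), as items 7 and 28 already have it, or section 4.2.2 (Visit 2, before the first dose). Visit 2 lies closer to the start of treatment, but no part of the protocol currently places the GASS there, so choosing it means changing items 7 and 28 too. Whichever visit is chosen, make Table 1, sections 4.2.1 and 4.2.2, and items 7 and 28 agree, and use that value as the baseline for any GASS comparison.

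In the same edit, reconcile section 4.2.3 (GASS at every visit from 3 to 7) with Table 1 (none at Visits 4 and 6), and the Visit 8 list in section 7.2.4 (no GASS) with Table 1 (marked at Visit 8).

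The cost is one short self-report form per patient, which two places in the protocol already call for at Screening, plus the text corrections.

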1.1.1 Dose Selection

Lumateperone capsules are approved in the US by the FDA for the treatment of schizophrenia in adults and for the treatment of depressive episodes associated with bipolar I or II disorder (bipolar depression) in adults, as monotherapy and as adjunctive therapy with lithium or valproate. The recommended dosage regimen is lumateperone 42 mg administered orally once daily. Several studies have shown that lumateperone has a

favorable safety profile, exhibiting a similar tolerance to placebo, with no significant adverse effects reported. The purpose of this study is to determine the efficacy and safety of once daily lumateperone 42 mg as an adjunctive therapy for the treatment of patients with a history of childhood abuse and MDD. Symptoms of depression may or may not improve during participation in this study; half of the patients in this study will receive placebo. However, the information obtained from this study may help to treat people suffering from MDD with history of childhood abuse.

2. Study Population

2.1 Inclusion Criteria

To be eligible to participate in the study, patients must meet the following inclusion criteria:

1. Provide written informed consent before the initiation of any study-specific procedures. See informed consent requirements;

NOTE: Patients who are unable to independently provide informed consent will be ineligible to participate in this study.

2. Male or female, between the ages of 21 and 70 years, inclusive;
3. Meets the Diagnostic and Statistical Manual of Mental Disorders, 5th Edition, Text Revision (DSM-5-TR) criteria for MDD without psychotic symptoms, as confirmed by a trained rater using the modified Structured Clinical Interview (DIAMOND) for DSM-5,
4. MADRS total score ≥ 22 at Screening (Visit 1) and Baseline (Visit 2)
5. Endorse ≥ 1 physical or sexual assault prior to age 16 on the interview-based trauma assessment.

Many studies refer to early life trauma as prior to age 18. Here we define early life assault as less than 16, rather than 18, in order to ensure a clearer separation between early life and adulthood. While another option might be to restrict even further (e.g., age of trauma < 10), for feasibility (e.g., facilitating recruitment) and generalizability (e.g., results extend to MDD and early life trauma more broadly than just early childhood trauma), we decided on physical or sexual assault prior to age 16.

Regarding the focus on physical or sexual assault, there are two main reasons. First, the definition of physical and sexual assault can more easily be operationalized through a behavioral description of an event (e.g., has anyone hit you with a fist, has anyone hit you with an object, etc), enabling more precise assessment and detection. Second, there is a robustly elevated risk for mood disorders following assaultive traumas relative to non-assaultive traumas. As such, there is greater clinical need to establish adjunctive treatments among those experiencing assaultive traumas.

6. Participants must have been treated with the same dose of antidepressant therapy for at least 6 weeks, with less than 50% improvement, and be committed to stay on the same stable dosing regimen for the Screening period and for the entire study, at or above the minimally adequate dose in the ATRQ. Documentation of stable and ongoing ADT must be verified by documentation from the subject's psychiatrist, pharmacist, primary care physician, or other qualified healthcare professional.
7. Females of childbearing potential agree to use at least an acceptable method of birth control (including but not limited to hormonal contraception, intrauterine device, vasectomized partner, bilateral tubal occlusion, condom with or without spermicide, cap with spermicide, diaphragm with spermicide, sponge with spermicide, or double barrier methods) from the time informed consent is provided through the end of the SFU period. *NOTE:* Females of non-childbearing potential (defined as either permanently sterilized, or post-menopausal females [defined as at least one year with no menses without an alternative medical explanation]) are exempt from the birth control requirement.
8. Ability to follow study instructions and likely to complete all required visits.

2.2 Exclusion Criteria

Patients who meet any of the following exclusion criteria will not be eligible to participate in the study.

Psychiatric Criteria

1. Has a **current primary** DSM-5-TR psychiatric diagnosis other than Major depressive disorder. These include:
 - i. PTSD, OCD, Bipolar Disorder, Schizophrenia, schizoaffective disorder, or other psychotic disorders;
 - ii. Intellectual disability, Dementia or other cognitive disorders;
 - iii. Moderate or severe substance use disorder (excluding for nicotine);
2. In the opinion of the Investigator, the patient has a significant risk for suicidal behavior during the course of his/her participation in the study or
 - i. At Screening (Visit 1), the patient scores “yes” on Items 4 or 5 in the Suicidal Ideation section of the C-SSRS within 6 months prior to Screening; or
 - ii. At Screening (Visit 1), the patient has history of suicidal attempt(s) within 1 year prior to Screening (Visit 1); or
 - iii. At Baseline/randomization (Visit 2), the patient scores “yes” on Items 4 or 5 in the Suicidal Ideation section of the C-SSRS since the Screening Visit; or
 - iv. At Screening (Visit 1) or Baseline (Visit 2), scores ≥ 4 on Item 10 (suicidal thoughts) on the rater administered MADRS; or
 - v. Considered to be an imminent danger to himself/herself or others.

Treatment-related Criteria:

3. MRI contraindications: History of shrapnel or other metal or electronic implants in the body(such as pacemakers, aneurysm clips, ferrous surgical devices, metallic tattoos on the head, etc.). The patient has received electroconvulsive therapy (ECT), vagal nerve stimulation, or repetitive trans-cranial magnetic stimulation within the past 1 year;
4. The patient has known hypersensitivity or intolerance to lumateperone, or to any of the excipients;
5. Treatment with a depot/long-acting injectable antipsychotic within 1 cycle before Screening (Visit 1);
6. The following agents are excluded and must be discontinued at Screening (Visit 1):
 - i. Any moderate or strong cytochrome P450 3A4 inhibitor (CYP3A4), or any CYP3A4 inducer;
 - ii. Central opioid agonists/antagonists, including tramadol;
 - iii. Anticonvulsants, mood stabilizers, antidepressants, stimulants, antipsychotics, and non-benzodiazepine anxiolytics;
 - iv. Dietary supplements and medical foods unless approved by the Sponsor or designee. Daily multivitamin use is permitted;
7. Monoamine oxidase inhibitors within 14 days prior to Baseline/Randomization (Visit 2);
8. Other drugs with known psychotropic properties or any non-psychotropic drugs with known or potentially significant central nervous system.
9. The patient plans to initiate psychotherapy or make changes to existing psychotherapy during the study (patients who are participating in stable psychotherapy or psychotherapy as a part of their treatment are allowed to enroll);
10. The patient has participated in a previous clinical trial with lumateperone, or has had exposure to any investigational product within 6 months of the baseline visit or participated in > 2 clinical studies

of an investigational product with a central nervous system indication.

Other Medical Criteria:

11. The patient is pregnant or breast-feeding. Female patients of childbearing potential must have a negative serum pregnancy test at Screening (Visit 1). On Day 1 (Baseline/Visit 2), female patients of childbearing potential must have a negative urine pregnancy test prior to study drug administration;
12. The patient has a positive test for alcohol or drugs of abuse (eg, amphetamines, barbiturates, benzodiazepines, cannabinoids, cocaine, methadone, or opioids/opiates) at Screening (Visit 1).
13. The patient has abnormal laboratory values or clinical findings at Screening (Visit 1) including, but not limited to:
 - i. Alanine aminotransferase (ALT) and/or aspartate aminotransferase (AST) $> 2 \times$ the upper limit of normal (ULN);
 - ii. Total bilirubin $> 1.0 \times$ ULN;
 - iii. Hemoglobin $< 8 \text{ g/dL}$ (80 g/L) for females and $< 9 \text{ g/dL}$ (90 g/L) for males;
 - iv. Absolute neutrophil count (ANC) $< 1200 \text{ cells}/\mu\text{L}$ ($1.2 \times 10^9 \text{ cells}/\text{L}$);
 - v. Thyroid-stimulating hormone (TSH) outside of normal reference range AND free T3 or free T4 outside of the reference range. Free T3 and Free T4 will only be evaluated if TSH is outside of reference range;
 - vi. Poorly controlled diabetes as defined by a glycosylated hemoglobin (HbA1c) $> 7.5\%$, despite standard care [$> 58 \text{ mmol/mol}$];
 - vii. Positive test for hepatitis B surface antigen and/or hepatitis B core antibody immunoglobulin M at screening; positive hepatitis C antibody at Screening (Visit 1), with the exception of a patient for whom the reflex HCV RNA test is negative;
 - viii. Any other clinically significant abnormal laboratory result obtained at screening (Visit 1);
14. ECG abnormalities where the patient has corrected QT interval using the Fridericia formula (QTcF) $> 450 \text{ msec}$ for males or $> 470 \text{ msec}$ for females and/or heart rate $< 50 \text{ bpm}$, or evidence of clinically significant bundle-branch blocks at Screening (Visit 1);
15. The patient has any of the following conditions:
 - i. Cardiac: uncontrolled angina, or history of a myocardial infarction within 3 months prior to screening, or history of a clinically significant cardiac arrhythmia including antipsychotic drug-induced corrected QT interval prolongation, or any other cardiac disorder;
 - ii. Malignancy: Any diagnosis of cancer (except basal or squamous cell skin carcinoma), unless in remission for at least 5 years;
 - iii. Gastrointestinal: history of gastric bypass or any other condition that results in malabsorption;
 - iv. Endocrine: hypo- or hyperthyroidism unless treated and stable with no medication changes for at least three months prior to screening, diabetes, unless considered stable with no changes in treatment for at least three months prior to screening;
 - v. Hepatic: Hepatitis B or Hepatitis C; moderate or severe hepatic impairment (Child-Pugh B or C);
 - vi. Pulmonary: history of diagnosed and untreated obstructive sleep apnea;
 - vii. Neurological: history of epilepsy, seizure or convulsion, or electroencephalogram with clinically significant abnormalities, delirium, dementia, amnesia, or central sleep apnea, or significant brain trauma, or other cognitive disorder; History of movement disorders.
 - viii. Infectious: History of human immunodeficiency virus (HIV) infection.

Note: Any other medical condition, or medical conditions that are stable with treatment (eg, hypertension, hypercholesterolemia, or thyroid abnormalities) are allowed as long as the condition has been stable for at least 3 months prior to Screening (Visit 1); treatments for these conditions are documented, kept stable, and are expected to be unchanged during the study; and the condition is

not thought to affect safe participation in the study or relevant study outcomes in the opinion of the Investigator.

Other Criteria:

16. The patient is judged by the Investigator to be inappropriate for the study;
17. Patient is homeless;
18. Patient does not speak english;

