Regarding the focus on physical or sexual assault, there are two main reasons. First, the definition of physical and sexual assault can more easily be operationalized through a behavioral description of an event (e.g., has anyone hit you with a fist, has anyone hit you with an object, etc), enabling more precise assessment and detection. Second, there is a robustly elevated risk for mood disorders following assaultive traumas relative to non-assaultive traumas. As such, there is greater clinical need to establish adjunctive treatments among those experiencing assaultive traumas.

14. Participants must have been treated with the same dose of antidepressant therapy for at least 6 weeks, with less than 50% improvement, and be committed to the same stable dosing regimen for the Screening period and for the entire study, at or above the minimally adequate dose in the ATRQ. Documentation of stable and ongoing ADT must be verified by documentation from the subject's psychiatrist, pharmacist, primary care physician or other qualified healthcare professional.

15. Female of childbearing potential and agrees to use at least an acceptable method of birth control (including but not limited to hormonal contraception, intrauterine device, vasectomized partner, bilateral tubal occlusion, condom with or without spermicide, cap with spermicide, diaphragm with spermicide, sponge with spermicide, or double barrier methods) from the time informed consent is provided through the end of the SFU period. **NOTE:** Females of non-childbearing potential (defined as either permanently sterilized, or post-menopausal females [defined as at least one year with no menses without an alternative medical explanation]) are exempt from the birth control requirement.

16. Ability to follow study instructions and likely to complete all required visits.

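### Exclusion 6.iii and its copy 24.iii list antidepressants among drugs to stop at Screening, while Inclusion 6 requires the same stable antidepressant throughout: a wording error whose intent is clear

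*Protocol*

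**What the plan says.** **The exclusion rule.** Protocol Section 2.2, item 6, opens "The following agents are excluded and must be discontinued at Screening (Visit 1"), and sub-item iii then lists "Anticonvulsants, mood stabilizers, antidepressants, stimulants, antipsychotics, and non-benzodiazepine anxiolytics". Item 24.iii, in the second copy of the criteria (form item 20, under the heading 4.3 Exclusion Criteria), has the same words under the same lead-in.

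**The inclusion rule.** Section 2.1, item 6, requires at least 6 weeks on the same antidepressant dose with less than 50% improvement, and the patient must "be committed to stay on the same stable dosing regimen for the Screening period and for the entire study". It adds: "Documentation of stable and ongoing ADT must be verified by documentation from" a treating professional. Item 14 of the second copy says the patient must "be committed to the same stable dosing regimen for the Screening period and for the entire study".

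**The nearest exception.** The Screening Period text in form item 7, repeated in form item 28, says: "With the exception of stable, allowed concomitant medications, patients must discontinue prohibited psychotropic drugs during the Screening Period".

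**The medication lists.** Section 3.7 permits medicines for extrapyramidal symptoms and akathisia, zolpidem, and lorazepam or other benzodiazepines. Section 3.7.1 prohibits psychotropic drugs apart from those listed in a Section 6.7.

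**The concern.** The two rules give opposite instructions about the same drug. One makes a stable, ongoing antidepressant a condition of entry. The other puts antidepressants as a class on the list of drugs to stop at the first visit. Both are operative criteria that staff check off for each patient, not background text.

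Two things are at stake. If staff follow the inclusion rule, each properly enrolled patient carries a breach of an exclusion criterion on paper, and genuine medication deviations become harder to pick out. If staff follow the exclusion rule, a depressed patient with a MADRS of at least 22 stops an antidepressant before Baseline. That is a safety matter in this population, and an eligibility rule should not instruct it.

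**Working it through.** There is no figure to reproduce. The check sets the texts side by side and looks for anything that reconciles them.

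| Text | What it requires of the background antidepressant |
|---|---|
| Inclusion 6 and its copy 14 | Same dose for at least 6 weeks, kept through Screening and the whole study, with outside documentation |
| Exclusion 6.iii and its copy 24.iii | Antidepressants, as a class, stopped at Visit 1 |
| Screening text, form items 7 and 28 | Exempts medicines that are both stable and allowed; does not name antidepressants |
| Section 3.7 | Lists permitted medicines; background antidepressant not among them |
| Section 3.7.1 | Prohibits other psychotropics, by reference to a Section 6.7 |

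**Step 1. Is there an exception inside the item?** No. Exceptions were written where they were wanted: sub-item 6.iv allows sponsor-approved supplements and a daily multivitamin, and item 1.iii exempts nicotine. Sub-item 6.iii has none.

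**Step 2. Does the Screening text supply one?** Not fully. It turns on what counts as allowed. The natural place to look is Section 3.7, which does not list the antidepressant. Section 3.7.1 then prohibits psychotropics that are not listed. Its reference to Section 6.7 matches no concomitant-medication section in the document and evidently means 3.7. Followed to its end, the exception arrives at a list without the required drug.

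**Step 3. Which rule reflects the intent?** Inclusion 6. Form items 6 and 17 describe inadequate response to SSRI treatment that is still ongoing. Form item 7 speaks of "subjects currently receiving approved dosing regimen of ADT". Section 11.3 defines the primary endpoint in patients taking an antidepressant plus study drug. All of these assume that the antidepressant continues.

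**Step 4. How far could the literal reading reach?** Table 1 places Screening up to 15 days before Baseline and has eligibility checked at both visits. Form item 6 and Section 4.2.2 allow randomization only of patients who still meet every criterion at Baseline. A patient who stopped the antidepressant at Visit 1 would no longer meet Inclusion 6 and would not be randomized. On that course the damage ends with Screening.

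**Step 5. What if the site follows the intent?** Every patient enrolled under Inclusion 6 is then in breach of 6.iii as worded. With the planned enrolment of 50, that is up to all 50.

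**The case against.** The strongest reply is that nobody would be misled. The trial is run at one site by the investigators who conceived it, the whole document describes adjunctive treatment, and Inclusion 6 is the specific rule while 6.iii merely names a class in a general list. A drug that the protocol requires to be stable is most naturally read as one of the stable, allowed medicines that the Screening text exempts. Section 3.7 also provides for recording treatments begun before the study, so it contemplates continuing medication.

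Much of this stands. It shows that the intent can be recovered, that the harmful course is unlikely, and that the error is not a blocking defect. It also shows that it is fair to say 6.iii has no exception only of the item itself. It does not remove the contradiction, because recording a medicine is not the same as allowing it, and no text lists the antidepressant as allowed.

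It is also fair to say that the two copies carry one error, repeated because the form gives the criteria twice.

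**Conclusion.** The point holds as a single drafting error in an operative eligibility rule, present in both copies of the criteria. It is wrong as written and should be fixed. The literal risk is confined to Screening, at most 15 days, plus a paper breach for each correctly enrolled patient. This rests on reading 6.iii as it is worded and on the Baseline recheck being carried out as Table 1 requires.

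Four stronger readings may tempt a reader, and the documents support none of them.

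- **Patients would go through the 6-week treatment period without their antidepressant.** The Baseline recheck stops such a patient from being randomized.
- **The estimate or power is affected.** Nothing in the text leads there, since patients off their antidepressant should not enter the randomized data.
- **Exclusion 8 and its copy 26 also bar the antidepressant.** Item 8 reads "Other drugs with known psychotropic properties or any non-psychotropic drugs with known or potentially significant central nervous system". Its first word sets aside the classes already handled in item 6, so it holds no present error, and antidepressants remain handled in 6.iii after the correction.
- **The required antidepressant would count as prohibited medication, the second intercurrent event in Section 11.3.** Section 3.7.1 read literally might suggest it, but the same section defines the endpoint in patients on an antidepressant, and Section 11.2 is concerned with newly started treatment for MDD.

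**What to change.** 1. In items 6.iii and 24.iii, replace the bare class name with *antidepressants other than the stable ADT required by the inclusion criteria*.
2. In Section 3.7, list that antidepressant as an allowed concomitant medication, so that the exemption in form items 7 and 28 has a defined meaning.
3. In Section 3.7.1, change the cross-reference from 6.7 to 3.7, so that the required drug is not caught by the prohibition.

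Exclusion 8 and its copy 26 need no change. The cost is a wording amendment to two exclusion lines and two medication sections. Design, sample size, visits and analysis stay as they are.
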